8.2.2.3 Responder outcome for all type seizure days

Responder outcome for all other type seizure days will be derived in a manner similar to the responder outcome for POS frequency as described in Section 8.1.3. This variable will be summarized in the same manner as 50% responder outcome for POS frequency.

8.2.2.4 Specified month seizure freedom

Specified month seizure freedom for subjects in the PGS Efficacy Analysis Set will be derived in a manner similar to specified month seizure freedom for the POS Efficacy Analysis Set as described in Section 8.2.1.1. This variable will be summarized in the same manner as specified month seizure freedom for subjects in the POS Efficacy Analysis Set.

8.2.3 QOLIE-31-P

The scoring algorithm for QOLIE-31-P is described in Section 13.1. QOLIE-31-P will be summarized for the POS and PGS Efficacy Analysis Sets. QOLIE-31-P is assessed at the following time points for subjects with POS and subjects with PGS: Month 2, Month 6, Month 12, Month 18, and Month 24. QOLIE-31-P is also assessed at EDVs for subjects who discontinue prior to the YEV at the end of the second year.

Observed values for QOLIE-31-P total score and subscale scores for Seizure Worry, Daily Activities/Social Function, Energy/Fatigue, Emotional Well-Being, Cognitive Function, Medication Effects, Overall Quality of Life, and Health Status will be summarized for Months 2, 6, 12, 18, and 24 and Last Value for the Efficacy Analysis Sets for POS and PGS. For each time point, summary statistics will be presented for the baseline scores for subjects with a change from baseline at the time point in addition to summaries of the observed values and changes from baseline at each time point. Only subjects with a non-missing change from baseline will be summarized at each time point.

The above scores will be also summarized for the 6-Month, 12-Month, 18-Month, and 24-Month Study Visit Cohorts, including summaries of the baseline scores for all subjects within each study visit cohort and summaries of observed values and changes from baseline for each time point for each study visit cohort.

Similar summaries will be provided for QOLIE-31-P distress items Seizure Worry, Daily Activities/Social Function, Energy/Fatigue, Emotional Well-Being, Cognitive Function, Medication Effects, Overall Quality of Life. Only subjects with a non-missing change from baseline will be summarized at that time point.

The rankings of prioritization items (Seizure Worry, Daily Activities/Social Function, Energy/Fatigue, Emotional Well-Being, Cognitive Function, Medication Effects, and Overall Quality of Life) will be summarized at the same time points as above and for all subjects and by study visit cohort as defined above. Changes from baseline will not be summarized, and only the numbers of subjects and sample means will be presented

8.2.4 Direct cost parameters

Direct costs data are collected based on concurrent medical procedures, healthcare provider consultations not foreseen by protocol, hospital stays, and ER visits

Direct cost parameters will not be summarized but will be provided in subject data listings.

8.2.5 Indirect cost parameters

The number of school or working days lost will not be summarized but will be provided in subject data listings.

8.2.6 Socio-professional data

Socio-professional data are collected at the following time points: Month 12 and Month 24. Socio-professional data are also collected at EDVs for subjects who discontinue prior to the YEV at the end of the second year. These additional assessments will not be summarized but will be provided in subject data listings.

9 PHARMACOKINETICS AND PHARMACODYNAMICS

Plasma samples to analyze BRV or concomitant AED plasma concentrations are not collected. As such, this section is not applicable.

10 IMMUNOLOGICAL PROCEDURES

This section is not applicable for this study.

11 SAFETY ANALYSES

Safety is assessed with AEs, laboratory tests (blood chemistry, hematology, urinalysis, endocrinology, and pregnancy test), vital signs, body weight, ECGs, physical examination, and neurological examination. Summary tables will be provided for AEs; blood chemistry, hematology, urinalysis, and endocrinology; vital signs; body weight; and ECGs. No summary tables will be provided for pregnancy testing, physical examination, and neurological examination.

All safety summaries will be based on the Safety Population.

11.1 Extent of exposure

A daily dose will be calculated for each study day from the day of first dose of BRV to the day of last dose of BRV for the purposes of calculating modal dose. Daily dose will be calculated as the sum of the AM and PM dose for each day.

Modal daily doses will be calculated across all study days on or after the day of first dose of BRV and up to and including the day of last dose of BRV. Modal daily dose is the most frequently taken daily dose during this period. In the event of a tie, the modal dose will be set to the lower of the tied doses. Modal daily dose will be categorized as follows:

Category	Definition
5 mg/day	<20mg/day
20mg/day	≥20mg/day to <50mg/day
50mg/day	≥50mg/day to <100mg/day
100mg/day	≥100mg/day to <150mg/day
150mg/day	≥150mg/day to <200mg/day
200mg/day	≥200mg/day

Subject years of exposure will be calculated by summing the exposure duration in days for all subjects being summarized, and dividing the resulting value by 365.25.

Subject years of exposure will be presented overall and by modal dose for the Safety Analysis Set. The subject years of exposure presented by modal dose will be the total subject years of exposure of subjects with that modal dose.

The number and percentage of subjects exposed to BRV will be summarized overall and by modal dose category. The number and percentage of subjects in each Exposure Duration Cohort (≥3 months, ≥6 months, ≥12 months, and so forth) will be summarized.

The number and percentage of subjects within each modal dose category will be summarized for each Exposure Duration Cohort; percentages will be relative to the total number of subjects in each Exposure Duration Cohort.

In addition to the overall summaries of the above, the above will also be summarized by subgroup for region (North America, Europe [EU member states], Europe [non-EU member states], Asia/Pacific/Other), and seizure type (Partial Onset Seizures, Primary Generalized Seizures).

11.2 Adverse events

11.2.1 Definition of treatment-emergent AE

AEs will be classified as either pre-study or treatment-emergent. Pre-study AEs are defined as AEs which had onset prior to the date of the first dose of BRV. TEAEs are defined as AEs that had onset on or after the day of first BRV dose. AEs with an incomplete onset date will be classified as TEAEs if the month and year of onset (when only the month and year are specified) is the same as the month and year of the first BRV dose or the year of onset (when only year is specified) is the same as the year of first BRV dose.

11.2.2 General summaries of TEAEs

Pre-treatment AEs will be provided in a subject data listing; no summaries of pre treatment AEs are planned.

An overall summary of AEs will provide the overall number of TEAEs and the numbers and percentages of subjects with at least 1 TEAE, with a TEAE that led to permanent discontinuation of study drug, with a drug-related TEAE, with a severe TEAE, with a treatment-emergent SAE, and with a drug-related treatment-emergent SAE. The number and percentage of subjects who died will also be summarized. This summary will be provided for all subjects in the Safety Analysis Set and also by subgroup for geographic region and seizure type.

The following summaries of TEAEs will be provided by MedDRA SOC and PT. All summaries are for the combined Evaluation, Down-Titration, and Post-Treatment Periods unless otherwise indicated.

Overall Incidence Summaries

- Incidence of TEAEs
- Incidence of TEAEs by 3-month time interval
- Incidence of TEAEs by study period (Evaluation, Down-Titration, Post-Treatment)
- Incidence of TEAEs for TEAEs occurring in at least 5% of subjects
- Incidence of TEAEs by 3-month time intervals for TEAEs occurring in at least 5% of subjects overall
- Incidence of non-serious TEAEs occurring in at least 5% of subjects

The incidence of TEAEs occurring in at least 5% of subjects will be summarized overall as noted above and also by subgroup for geographic region, seizure type, and randomized treatment from the previous double-blind study.

A subject is included in a 3-month interval if the subject was receiving BRV at any time during that interval based on their duration of exposure to BRV (eg, a subject with exposure for 91 days is included in the time interval for Months 1-3 and Months 4-6). Summaries of AEs by 3-month intervals will include all subjects who are classified into each time interval as defined above. TEAEs which had onset prior to or on the date of the last dose of BRV) are included in summaries by 3-month time intervals.

Maximum Intensity and Causality

- Incidence of TEAEs by maximum intensity
- Incidence of drug-related TEAEs

Serious Adverse Events

- Incidence of treatment-emergent SAEs

Discontinuations due to TEAE

- Incidence of TEAEs leading to permanent discontinuation of study drug

TEAEs of interest

AEs of interest will be identified based on MedDRA search criteria, which are documented outside of the SAP. The following summaries will be provided for AEs of interest:

- Incidence of TEAEs of interest
- Incidence of TEAEs of interest by 3-month time interval

For the summary by maximum intensity, each subject will be counted at most once per SOC or PT according to the maximum intensity of all AEs within that SOC or PT. Severe intensity will be assumed for AEs for which intensity is not specified.

Drug-related AEs are AEs for which the relationship to study drug is specified as Related or AEs for which relationship is not specified.

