5.1.2 Planned number of subjects and sites

It is estimated that approximately 650 to 720 subjects from N01358 will enter the study, based on the assumption that at least 90% of randomized subjects from N01358 will complete N01358 and enroll in N01379. Up to 100 subjects from N01258 may also be eligible for enrollment.

It is estimated that 120 sites from N01358 and up to 25 sites from N01258 will participate in the study.

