2.3 Study Design and Conduct

This is an open-label, long-term follow-up, multicenter, noncomparative, single-arm study of BRV. The primary objective is to evaluate the long-term safety and tolerability of BRV at individualized doses up to a maximum of 200mg/day in subjects with epilepsy. The secondary objective is to evaluate the maintenance of efficacy of BRV. Exploratory objectives are to assess the effects of BRV on subjects' HRQoL, obtain information on the direct costs, explore changes in socio-professional status, and assess the role of gene variants of SV2. DNA analysis will only be done for those subjects coming from N01358.

Study N01379 enrolled subjects 16 years of age and older who had completed N01358 or N01258. Study N01358 enrolled subjects with refractory partial onset seizures (POS) whether or not secondarily generalized and N01258 enrolled subjects with localization-related or generalized epilepsy (designated as "PGS subjects").

Subjects from N01258 were started at an oral dose of BRV 200mg/day (2 equally divided doses administered twice daily) and should be maintained at this dose for at least 2 weeks unless the subject is unable to tolerate treatment. Subjects from N01358 were started on oral BRV at a dose of 150mg/day (2 equally divided doses administered twice daily) at study entry and should be maintained at this dose for at least 2 weeks unless the subject was unable to tolerate treatment.

Subjects who enroll in the study entered an Evaluation Period during which treatment with BRV was initiated. The dose of BRV can be adjusted based on the individual subject's seizure control and tolerability. Dose increases can be made in increments of 50mg/day on a weekly basis up to a maximum of 200mg/day; dose decreases can be made in steps of 50mg/day on a weekly basis. Subjects who discontinue treatment with BRV enter a Down-Titration Period during which the dose of BRV is decreased in steps of 50mg/day on a weekly basis with a last down-titration step at 20mg/day for 1 week. Subjects who have completed the Down-Titration Period or subjects who discontinue during the Evaluation Period without entering the Down-Titration Period enter a Post-Treatment Period for a minimum of 2 weeks and a maximum of 4 weeks.

The maximum allowable daily dose for this study is 200mg/day based on the protocol. It is recommended that the daily dose be administered in 2 equal intakes.

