3.2 Analysis time points

3.2.1 First and last dose of BRV

Unless otherwise noted, all references to the first dose of BRV in this SAP refer to the first dose of BRV during N01379 (ie, not the first dose of BRV from the previous study in which subjects participated in prior to N01379). Unless otherwise noted, all references to the last known dose of BRV in this SAP refer to the last dose of BRV taken across any study periods (ie, not necessarily the last dose of BRV during the Evaluation Period).

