3.5.2 Efficacy populations

Efficacy Populations will consist of all subjects who took at least 1 dose of study drug and have at least 1 seizure diary day during the Evaluation Period. Separate Efficacy Populations are defined for subjects with focal epilepsy from N01358 and N01258 and subjects with generalized epilepsy from N01258.

A subject will be excluded from the Efficacy Analysis Set for POS or PGS if either they did not receive at least 1 dose of BRV, or the clinical database indicates that the daily seizure diary was not completed for any days on or after the first dose of BRV and on or prior to the end date of the Evaluation Period (see Section 8). Subjects were assigned to a POS population or a PGS population in the previous study, based on diagnosis or medical history.

Seizure outcomes will be summarized for either the Efficacy Population for POS or the Efficacy Population for PGS. Summaries of epilepsy history and QOLIE-31-P will be provided for the Efficacy Populations for both POS and PGS.

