4.8 Examination of subgroups

Selected summaries will be provided for the following subgroups as specified within each of the following sections:

- Two mappings of countries to regions are defined, 1 based on the classification requested by Food and Drug Administration (FDA), and 1 based on the regional classification for the CHMP (Committee for Medicinal Products for Human Use).

Countries will be mapped to geographic regions as follows for the FDA:

Geographic Region (FDA)	Country
North America	Canada, United States, Puerto Rico
Latin America	Brazil, Mexico
Western Europe	Austria, Belgium, Finland, France, Germany, Ireland, Italy, Netherlands, Norway, Réunion, Spain, Sweden, United Kingdom, Switzerland
Eastern Europe	Bulgaria, Czech Republic, Estonia, Latvia, Hungary, Lithuania, Poland, Romania, Russia, Serbia and Montenegro, Turkey, Ukraine
Asia/Pacific/Other	Australia, Hong Kong, India, Israel, Japan, Singapore, South Africa, Republic of Korea, Taiwan, Tunisia

Countries will be mapped to geographic regions as follows for the CHMP:

Geographic Region (CHMP)	Country
North America	Canada, United States, Puerto Rico
Latin America	Brazil, Mexico
Europe (European Union [EU] member states) *	Austria, Belgium, Bulgaria, Czech Republic, Estonia, Finland, France, Germany, Hungary, Ireland, Italy, Latvia, Lithuania, Netherlands, Norway, Poland, Réunion, Romania, Spain, Sweden, United Kingdom
Europe (non-EU member states)	Russia, Serbia and Montenegro, Switzerland, Turkey, Ukraine
Asia/Pacific/Other	Australia, Hong Kong, India, Israel, Japan, Singapore, South Africa, Republic of Korea, Taiwan, Tunisia

* EU member states plus Norway.

- Seizure type (Partial Onset Seizures, Primary Generalized Seizures)
- Randomized treatment in the previous study (placebo [PBO], BRV) (TEAEs only)

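### AE tables by seizure type are almost fully confounded with core study: generalized subjects all come from N01258, and about 87–100% of focal subjects come from N01358

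*SAP*

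**What the plan says.** **Tables by seizure type.** SAP 11.2.2 lists an overall AE summary that contains the three primary safety variables of Protocol 4.1.1 (TEAEs, SAEs, withdrawal due to AE). It then says: "This summary will be provided for all subjects in the Safety Analysis Set and also by subgroup for geographic region and seizure type". The table of TEAEs seen in at least 5% of subjects is also repeated by seizure type. SAP 4.8 lists region, seizure type and prior randomized treatment as subgroups. Core study (N01358 or N01258) is not among them.

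**Where the groups come from.** SAP 3.5.2: "Separate Efficacy Populations are defined for subjects with focal epilepsy from N01358 and N01258 and subjects with generalized epilepsy from N01258". SAP 2.3: "Study N01358 enrolled subjects with refractory partial onset seizures (POS) whether or not secondarily generalized". Protocol 5.1.2 expects about 650 to 720 entrants from N01358, and: "Up to 100 subjects from N01258 may also be eligible for enrollment".

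**How they enter.** SAP 3.2.3 places entry at Week 2 of N01258 and Week 20 of N01358, with no break in dosing. On starting dose, SAP 2.3 says: "Subjects from N01258 were started at an oral dose of BRV 200mg/day". N01358 subjects start at 150 mg/day. Both starting doses are to be kept for at least 2 weeks where tolerated (Protocol 7.2).

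**When AEs start to count.** SAP 11.2.1 counts AEs from the first BRV dose. SAP 3.2.1 defines that as the first dose in N01379, "not the first dose of BRV from the previous study in which subjects participated in prior to N01379". AEs still ongoing from the core study are not recorded again unless intensity or seriousness changes (Protocol 8.1).

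**Placebo/BRV split.** SAP 4.8 describes it as "Randomized treatment in the previous study (placebo [PBO], BRV) (TEAEs only", while SAP 11.2.2 ties it to the earlier double-blind study. Protocol 7.9 calls N01358 double-blind and N01258 open-label.

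**The concern.** The primary objective is long-term safety, so these are main results of the study. A reader who sees a generalized column beside a focal column will take any gap as information about seizure type. Yet the columns also differ in core study, and core study brings three things that can move AE and withdrawal rates:

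- **Prior BRV exposure.** Generalized subjects have had at most about 2 weeks in N01258. Focal subjects from N01358 arrive at Week 20, either already treated with BRV or coming from placebo and new to it.
- **Tolerability filter.** Only subjects who completed the core treatment or evaluation period may enrol (Protocol 6.1, criterion 3). N01358 subjects on BRV have passed a longer filter, which bears directly on withdrawal due to AE.
- **Starting dose.** 200 against 150 mg/day for at least the first 2 weeks.

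No planned AE table separates core study. The 3-month AE intervals do not help, because they too start at the first N01379 dose (SAP 3.2.5). A core-study effect could therefore be reported as a difference in harms between seizure types. The SAP does recognise that N01258 differs for efficacy: section 8 takes its subjects out of percent reduction and responder rates, because of the short Baseline and the absence of a seizure-frequency requirement. Safety has no equivalent handling.

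**Working it through.** **1. The plan's own figure.** Protocol 5.1.2 gives 650 to 720 entrants from at least 90% rollover. Reading 720 as the number randomized (an assumption, since the documents do not state it), 0.90 × 720 = 648, which agrees with 650.

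**2. Share of focal subjects from N01358.** Let N be the number of N01358 entrants and F the number of focal N01258 entrants. F lies between 0 and 100; the documents do not give the split. Share s = N / (N + F).

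| N | F | s |
|---|---|---|
| 650 | 100 | 650/750 = 86.7% |
| 650 | 50 | 650/700 = 92.9% |
| 650 | 0 | 650/650 = 100% |
| 720 | 100 | 720/820 = 87.8% |

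So s is about 87% to 100%. The lowest value needs every N01258 subject to be focal, which would leave no generalized column, so realistic values lie higher. In the generalized group the N01358 share is 0%.

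**3. Starting dose.** Generalized mean: 200 mg/day. Focal mean: 150s + 200(1 − s), which is 150 mg/day at s = 1 and 156.7 mg/day at s = 0.867. The gap is 43.3 to 50 mg/day over the initial 2 weeks.

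**4. How much of a core-study difference passes through.** Suppose seizure type has no effect. Let A be the AE rate in N01358 subjects and B the rate in N01258 subjects.

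- Generalized column: B
- Focal column: sA + (1 − s)B
- Generalized minus focal: s(B − A)

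Between 86.7% and 100% of any core-study difference would show as a seizure-type difference. For an assumed 10-point difference, that is 8.7 to 10 points.

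**5. Can the sign or size of B − A be derived?** Let e be the risk of an early AE on starting BRV, f the fraction of that risk still to come when an N01258 subject enters N01379, and p the share of N01358 entrants who had placebo. Take BRV-treated N01358 entrants as past the early period. Early events inside the window are then f·e for N01258 and p·e for N01358, a difference of (f − p)e. None of e, f or p is in the documents. With p = 1/3 (assuming equal arms), the difference runs from −e/3 at f = 0 to +2e/3 at f = 1 and changes sign at f = 1/3. Dose changes at entry (from 100 or 200 to 150 mg/day for the BRV arms of N01358, none for N01258) and the completion filter add further unknown terms. Neither size nor direction can be derived.

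**6. Precision of the contrast within N01258.** Assume a 50/50 split of 100 subjects and 15% incidence. The standard error is √(2 × 0.15 × 0.85 / 50) = 0.071, so the 95% interval is about ±14 points.

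**The case against.** **The study is noncomparative and descriptive.** SAP 3.1 plans no testing, and no difference between seizure types is calculated. This stands: the issue is how a display will be read, not a faulty inference. It still concerns the display of the primary safety variables.

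**A reader might infer that the two groups have different TEAE windows.** They do not. The opening rule, the three study periods and the visit schedule are the same for all. What differs is the treatment history before the window opens.

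**A reader might also infer that generalized subjects will look worse.** The documents do not support that. N01258 subjects have already had their first BRV doses before entry, and former placebo subjects from N01358 start BRV entirely inside the window, so the artefact could go either way (working, step 5).

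**Other tables give context.** Exposure, subject-years and modal dose are summarized by seizure type (SAP 11.1), and common TEAEs by prior randomized treatment. This is partial help. None of them isolates core study or links dose to AEs by core study.

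**The contrast within N01258 is too small to be informative.** Largely true. An interval of about ±14 points will not settle whether harms differ. The split still shows that the generalized column has no N01358 subjects and lets it be set beside subjects with the same entry point and starting dose.

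**The placebo/BRV split is already limited to N01358.** SAP 11.2.2 read with Protocol 7.9 can be taken that way. A reader of SAP 4.8 alone might infer that N01258 subjects join the BRV column, but the SAP does not say so. What remains is a wording inconsistency.

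**Conclusion.** The concern holds as a structural one. In the AE tables by seizure type, seizure type and core study can hardly be told apart: the generalized group is 0% N01358 and the focal group about 87% to 100%. These shares rest on planning estimates and an unstated focal/generalized split in N01258, so 87% is a rounded planning value and not a guaranteed lower bound. If SAP 2.3 is read as labelling all N01258 subjects generalized, against SAP 3.5.2, the confounding is complete.

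With no true seizure-type effect, nearly all of any core-study difference in AE or withdrawal rates would appear as a seizure-type difference. How large that difference is, and which group it would favour, is not known. The starting-dose contrast is fixed only for about the first 2 weeks, after which dosing is individualized. The tables remain valid as descriptions of the subjects in them. The remedy is cheap and worth making, but nothing here calls the study's overall safety results into question.

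**What to change.** In SAP 4.8 and 11.2.2:

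- In the AE summaries by seizure type, show three columns: POS from N01358, POS from N01258, and PGS from N01258. A POS total may be kept.
- State that any focal-versus-generalized reading rests on the two N01258 columns, is descriptive, and is imprecise, with at most about 100 subjects in total.
- Word the placebo/BRV split the same way in both sections, explicitly limited to subjects from N01358.

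Core study is known for every subject, so no new data are needed. The cost is SAP wording and one extra column with small numbers in tables already planned.

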5.1.1 Study duration per subject

Subject recruitment for the study will begin in approximately Q2 2011. For each subject, the study will last from study entry until either regulatory approval of BRV has been granted by any Health Authority in an indication of adjunctive treatment of POS, until the Sponsor decides to close the study; until subjects transition to another BRV study; until a managed access program, named patient program, compassionate use program, or similar type of access program is established as allowed per country-specific requirement in addition to legal and regulatory guidelines; or until BRV development is stopped by the Sponsor.

The following study periods are defined:

- Evaluation Period (Visit 1 until the Last Evaluation Period Visit or Early Discontinuation Visit [EDV]): Subjects who enroll in N01379 will immediately enter the Evaluation Period.
- Down-Titration Period (up to 4 weeks)
 - If the subject is discontinuing study drug, the Investigator will first plan an EDV followed by the progressive down-titration of study drug.
 - During the Down-Titration Period, the BRV dose may be decreased in steps of a maximum of 50mg/day on a weekly basis. A last down-titration step at 20mg/day for 1 week should be included prior to the Posttreatment Period.
- Posttreatment Period (2 to 4 weeks): After completion of the Down-Titration Period, or for those subjects who for extenuating circumstances do not complete a Down-Titration Period, the subject will be required to enter a Posttreatment Period for a minimum of 2 weeks and a maximum of 4 weeks, followed by a Final Visit (FV).
- The end of the study is defined as the date of the last visit of the last subject in the study.

For subjects who transition to another BRV study or a managed access program or similar type of program or who will be converted to commercial BRV if, when, and where available, the Down-Titration Period and FV are not applicable.

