3.2.5 Monthly time intervals

A month is defined as 30 days and time intervals based on monthly durations are defined as a multiple of 30 days (eg, 12 months is defined as 360 days). The following definitions of 3-month and 6-month intervals are based on 30-day months where the date of first dose of BRV is Day 1:

Interval	Duration Definition
Months 1-3	Days 1-90
Months 4-6	Days 91-180
Months 7-9	Days 181-270
Months 10-12	Days 271-360
Months 1-6	Days 1-180
Months 7-12	Days 181-360
Months 13-18	Days 361-540
Months 19-24	Days 541-720

Subsequent 3- and 6-month intervals are defined in a similar manner.

Six-month intervals are defined for the evaluation of direct and indirect cost parameters.

Statistical summaries for direct and indirect cost parameters will only present results through the first 2 years of treatment. Three-month intervals will be used for analysis of efficacy outcomes and AEs.

For the analysis of efficacy outcomes, a subject is included in the analysis for a 3-month interval if the end date is on or after the *last day* of the 3-month interval and the subject diary was completed for at least 1 day during the 3-month interval.

For the analysis of AEs, a subject is included in the analysis for a 3-month interval if the end date is on or after the *first day* of the 3-month interval.

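### The 3-month AE tables give a subject with one day on BRV the same weight as one with 90, so apparent incidence drifts down in intervals where many subjects' exposure ends

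*SAP*

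**What the plan says.** SAP 11.2.2 lists TEAE incidence by 3-month interval for all TEAEs, for TEAEs in at least 5% of subjects, and for TEAEs of interest. The membership rule is "A subject is included in a 3-month interval if the subject was receiving BRV at any time during that interval", with the example that "a subject with exposure for 91 days is included in the time interval for Months 1-3 and Months 4-6". The denominator is everyone who qualifies: "Summaries of AEs by 3-month intervals will include all subjects who are classified into each time interval as defined above". The numerator is limited to "TEAEs which had onset prior to or on the date of the last dose of BRV".

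SAP 3.2.5 states the same rule through an end date: for AEs it is enough that the "end date is on or after the *first day* of the 3-month interval". For efficacy it asks for more: the "end date is on or after the *last day* of the 3-month interval".

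SAP 11.1 presents subject-years overall, by modal dose, and by region and seizure type, but not by 3-month interval. No exposure-adjusted AE rate is planned.

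Follow-up has no fixed length per subject. Protocol 5.1.1 ends it on approval, on transition to another study or an access program, when development stops, or "until the Sponsor decides to close the study".

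**The concern.** Intervals are counted from each subject's own first dose, while the study closes on the calendar. If entry is staggered, subjects still on BRV at closure are cut off part-way through different intervals. In the late intervals a growing share of the denominator, and in the last one everybody, has been at risk for less than 90 days but counts in full. Ordinary dropout has the same effect on a small scale throughout.

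The primary objective is long-term safety and tolerability, and the natural question of an interval table is whether risk changes with time on drug. Protocol 12.3 planned TEAE incidence by categories of total exposure duration, but SAP 11.2.2 lists no such table. Its table by study period separates treatment phases only. The 3-month tables are therefore the only TEAE summary by time on BRV in the SAP. A decline in them could be read as falling risk, or a late rise could be damped, when only the time at risk has changed.

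**Working it through.** **The plan's own example.** A subject belongs to interval k if exposure is at least 90(k − 1) + 1 days (a month is 30 days, SAP 3.2.5). For k = 2 this is 91 days, so 91 days of exposure gives Months 1-3 and Months 4-6, as the SAP says. The second membership rests on one day.

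**Formula.** Let p be the true 90-day risk, with constant hazard λ = −ln(1 − p)/90. Let a share f of included subjects have their last dose spread evenly over days 1 to 90 of the interval, independently of AEs. Then

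apparent incidence = (1 − f)·p + f·mean over d of [1 − exp(−λd)],

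which is close to p(1 − f/2).

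**Numbers.** Take p = 10% (assumed). Then λ = −ln(0.9)/90 = 0.001171 per day, and one day at risk carries a risk of 0.12%. The mean in the second term is 5.14%.

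| Share ending in the interval, f | Apparent incidence | Ratio to true |
|---|---|---|
| 3% | 9.85% | 0.985 |
| 5% | 9.76% | 0.976 |
| 20% | 9.03% | 0.903 |
| one third | 8.38% | 0.838 |
| 50% | 7.57% | 0.757 |
| 100% | 5.14% | 0.514 |

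At f = 100% the ratio is 0.507 for p = 2%, 0.548 for p = 40% and 0.581 for p = 60%. Common events therefore lose somewhat less.

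**Calendar closure (simulation).** The documents give a start of about Q2 2011 (Protocol 5.1.1) and an expected size of 650 to 720 plus up to 100 (Protocol 12.9). They do not give accrual length, dropout, closure date or AE risk. Assumed: N = 750, p = 10%, uniform entry over 24 months, one closing date at month 84, and 3% dropout per interval.

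| Interval | n | Share ending | Ratio to true |
|---|---|---|---|
| 1 to 20 | 750 falling to 420 | 3% | 0.985 |
| 21 | 407 | 15% | 0.926 |
| 25 | 180 | 27% | 0.866 |
| 26 | 131 | 35% | 0.826 |
| 27 | 84 | 51% | 0.746 |
| 28 (last) | 41 | 100% | 0.504 |

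Range over other assumptions:
- Closure at month 60 with 5% dropout gives 0.976 early and 0.818, 0.740 and 0.501 in the last three intervals (n about 117, 74 and 35).
- Entry over 6, 12 or 36 months (closure at month 84, 3% dropout) leaves the last two ratios at about 0.75 and 0.50, with n about 163, 82 and 27 in the last interval.
- Entry within 3 months affects only the last interval (0.504), but with n about 326.

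**Does person-time repair it?** With time censored at the first event in the interval, expected events equal λ times expected time at risk, whatever the spread of d. The rate is then λ × 365.25 × 100 = 42.8 per 100 subject-years in every interval, the last included.

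With uncensored interval time, a completed interval gives 0.10 × 365.25/90 × 100 = 40.6. A final interval, with mean time 45.5 days, gives 0.0514 × 365.25/45.5 × 100 = 41.3. These are close enough for single preferred terms. At p = 60% the same two figures are 0.60 × 365.25/90 × 100 = 243.5 and 0.3485 × 365.25/45.5 × 100 = 279.8, so censoring matters for any-TEAE.

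**The case against.** The SAP states the rule openly, with an example, and contrasts it with the efficacy rule. It keeps subjects who stopped early because of an AE, whom a completers-only rule would remove. Everything is descriptive, and the exposure-cohort counts and Kaplan-Meier retention show attrition. All of this stands, but none of it gives the time at risk within an interval.

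The bias is also small against noise where it is largest. At a true 10%, one binomial standard error is √(0.09/n): 2.6, 3.3 and 4.7 points for n = 131, 84 and 41, against biases of about 1.7, 2.5 and 5.0 points. Any single late interval is therefore inconclusive. However, the bias has the same sign in every interval, so it forms a trend, and with short accrual the last interval need not be sparse.

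The model assumes one closing date and stopping unrelated to AEs. Access programs and transitions may end follow-up at different times by country. Subjects who stop because of an AE bring an event into a short interval, which offsets part of the bias. That offset is weakest at administrative closure, which has nothing to do with AEs.

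A reader might infer three stronger things that the documents do not support:
- *That a constant risk would look as if it halves over the late study.* At p = 10%, a ratio of 0.55 or less needs about 93% of included subjects to end within the interval. In practice that is the last interval only.
- *That the primary safety results are biased.* The primary variables are occurrence of a TEAE, withdrawal due to AE, and occurrence of an SAE. Their overall incidence tables do not use the interval rule, and no by-interval table of SAEs or discontinuations is listed.
- *That late events disappear.* Every TEAE still counts in the overall tables. Only the interval percentage is lowered.

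**Conclusion.** The point holds as a limited but systematic bias in the by-interval TEAE and TEAEs-of-interest tables. The relative shortfall is about half the share of included subjects whose exposure ends in the interval. It is negligible early (1.5% to 2.5% with 3% to 5% dropout). Under staggered entry and one calendar closure it grows to about 17%, 25% and 50% over the last three intervals, which may hold few subjects.

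The mechanism follows from the SAP's wording. The sizes rest on constant risk, AE-independent stopping, and assumed accrual, dropout, closure date and AE risk, and AE-driven stopping would reduce them. As planned, a late decline in these tables cannot be told apart from shorter time at risk.

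**What to change.** In SAP 11.2.2, for each 3-month interval, add the number of subjects completing the interval and the subject-years on BRV within it. Next to n (%), report subjects with an event per 100 subject-years. For overall any-TEAE and for TEAEs of interest, censor time at the first event in that interval. For individual preferred terms, total interval subject-years are an acceptable approximation and avoid a separate denominator per term. State that any comment on change in risk over time will rest on these rates.

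Switching to the efficacy rule is not a substitute, because it would drop subjects who stopped for an AE.

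No new data are needed and the planned tables stay. The cost is modest extra programming, since SAP 11.1 does not compute subject-years by interval. Late-interval figures will look less favourable than the percentages, and will be imprecise where n is small.
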